During the iv PK Period, iv BRV will be administered every 12 hours ± 2 hours (q12h ± 2 h). All subjects will receive 1 to 2 consecutive doses of BRV; however, based on medical need, subjects may receive up to 10 consecutive doses of iv BRV. Blood sampling for PK analyses (herein referred to as "PK sampling") will occur with the first iv BRV administration and with 1 other iv BRV administration. For OLB, RxB, and IOB subjects, the first iv BRV dose will be equivalent

(mg-to-mg) to the final dose of oral BRV prior to the first iv dose. For IIB subjects, the first iv BRV dose will be 1mg/kg, not to exceed 50mg for subjects with body weights ≥ 50 kg. For all subjects, iv BRV doses may be adjusted at the Investigator's discretion after PK sampling for 2 iv doses; however, no doses may exceed the maximum doses indicated below. During the iv PK Period, BRV may only be administered by iv infusion.

At the completion of the iv PK Period, subjects who will continue oral BRV treatment should enroll in a long-term, open-label BRV study. Subjects who have received ≥ 4 doses of BRV and do not plan to continue treatment with BRV after completion of the iv PK Period or who discontinue BRV treatment during the study will have a Down-Titration Period of up to 4 weeks (28 days) for gradual discontinuation of BRV and a Safety (BRV-free) Period of 2 weeks (14 days) after the final dose of BRV. Subjects who have received < 4 doses of BRV may have BRV down titrated at the discretion of the Investigator.

For IOB and IIB subjects, the maximum BRV dose is 4mg/kg/day (2mg/kg twice daily [bid]). For OLB and RxB subjects, the maximum BRV dose is 5mg/kg/day (rounded) in recognition of the possibility that some of these subjects may be using this dose when they enter EP0065.

Throughout the study, no subjects may receive a dose greater than BRV 200mg/day. Oral BRV will be administered in equally divided doses bid.

It is planned for approximately 50 enrolled subjects to receive iv BRV in the following age-based cohorts (approximately 12 subjects/cohort), with approximately half of the subjects in each cohort receiving iv BRV as a 15-minute (± 3 minutes) infusion and half receiving iv BRV as a bolus (up to 2-minute infusion).

- Cohort 1: ≥ 12 to < 16 years
- Cohort 2: ≥ 6 years to < 12 years
- Cohort 3: ≥ 2 to < 6 years
- Cohort 4: 1 month to < 2 years

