^l To be collected as needed for IOB subjects who will enter the long-term, open-label study. To be dispensed, as needed, for subjects continuing into the Down-Titration Period at the final visit of the PK Period.

Table 5–1: Schedule of Study Assessments (Screening Period through end of iv PK Period)

Period	Screening	IOB Treatment	iv PK	TC-1	Unsch ^a
Visit	V1	V2	V3 to V12		
Study Day for					
OLB, RxB, IIB subjects	-10 to -1	N/A	1 to 6	2 to 9	N/A
IOB subjects	-20 to -11	-10 to -1			

Table 5–2: Schedule for iv PK Period ECGs, vital signs, and PK sampling (15-min BRV infusion)

Assessment	Time relative to initiation of iv BRV infusion							
	Pre-initiation	Post-initiation						
	≤ 1hr	5min (±1min)	10min (±1min)	15min ^a (±2min)	30min (±5min)	60min (±10min)	2hr (±15min)	3hr (±15min)
12-lead ECG	X	X	X	X	X	X	X	
Vital signs (BP, pulse rate, RR, temperature)	X	X	X	X	X	X	X ^c	
PK sampling ^b	X			X				X

BP=blood pressure; BRV=brivaracetam; ECG=electrocardiogram; hr=hour(s); min=minute(s); iv=intravenous; PK=pharmacokinetic; PCS=possibly clinically significant; RR=respiratory rate

^a To be conducted at the end of infusion.

^b Blood samples for PK analyses will be collected for the initial BRV infusion and 1 subsequent BRV infusion only. Blood samples should be collected after completion of the ECG and the vital sign measurements and from a region of the body not used for iv the BRV administration.

^c Only BP to be collected at 2 hours post initiation of infusion. Additional vital sign monitoring, specifically BP is necessary if a low PCS BP value occurs at 2 hours after the start of an infusion.

Table 5–3: Schedule for iv PK Period ECGs, vital signs, and PK sampling (bolus [up to 2-min BRV infusion])

Assessment	Time relative to initiation of iv BRV administration							
	Pre-initiation	Post-initiation						
	≤ 1hr	≤ 2min ^a	5min (±1min)	15min (±2min)	30min (±5min)	60min (±10min)	2hr (±15min)	3hr (±15min)
12-lead ECG	X	X	X	X	X	X	X	
Vital signs (BP, pulse rate, RR, temperature)	X	X	X	X	X	X	X ^c	
PK sampling ^b	X			X				X

BP=blood pressure; BRV=brivaracetam; ECG=electrocardiogram; hr=hour(s); min=minute(s); iv=intravenous; PK=pharmacokinetic; PCS=possibly clinically significant; RR=respiratory rate

^a To be conducted during bolus/infusion, if feasible.

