12.4 Planned safety analyses

Safety data will be reported in epochs that include the pre-bolus/infusion period(s), the bolus/infusion period(s), the period(s) immediately post-bolus/infusion, and period(s) between each subsequent bolus/infusion(s). These data will include vital signs, ECGs, and AE reporting.

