12.4.1 Analysis of safety variables

Descriptive statistics for the safety variables will be presented by cohort and infusion duration, cohorts overall, and all subjects overall. Additional summaries will include a summary of the OLB, RXB, IOB, and IIB groups by cohort and infusion duration.

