## 3 DATA ANALYSIS CONSIDERATIONS

### 3.1 General presentation of summaries and analyses

Statistical analysis and generation of tables, figures, subject data listings, and statistical output will be carried out using SAS Version 9.3 or higher. All summaries will be descriptive; no statistical hypothesis testing is planned. All tables and listings will use Courier New font size 9.

Tables, figures and listings (TFL) will be displayed for the defined analysis sets. If the Safety Set (SS) and the Safety Set-iv (SS-iv) consist of the same number of subjects, TFLs will only be presented for the SS-iv.

For categorical parameters, the number and percentage of subjects in each category will be presented. The denominator for percentages will be based on the number of subjects appropriate for the purpose of the analysis. Unless otherwise noted, all percentages will be displayed to 1 decimal place. No percentage will be displayed for zero counts, and no decimal will be presented when the percentage is 100%.

For continuous parameters, descriptive statistics will include number of subjects (n), mean, standard deviation (SD), median, minimum, and maximum, unless otherwise stated.

Decimal places for descriptive statistics will always apply the following rules unless otherwise stated:

- “n” will be an integer
- Mean, SD, geometric mean, and median will use 1 additional decimal place compared to the original data
- CV [%] will be presented with 1 decimal place
- Minimum and maximum will have the same number of decimal places as the original value

However, the maximum number of decimals displayed will not exceed 4.

All summaries, unless otherwise stated, will be presented overall for all subjects, by age cohorts (Cohort 1:  $\geq 12$  to  $< 16$  years, Cohort 2:  $\geq 6$  years to  $< 12$  years, Cohort 3:  $\geq 2$  to  $< 6$  years, Cohort 4:  $\geq 1$  month to  $< 2$  years), and by infusion duration (15-minute iv infusion and iv bolus (up to 2-minute infusion)). Selected tables will be provided in addition by subject groups (OLB, RxB and IOB combined, and IIB), or by scheduled assessment timepoints as defined in [Section 4.8](#).

Selected summaries will be repeated by the country of enrollment (Hungary and rest of the World).

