### **3.10 Changes to protocol-defined analysis**

As iv BRV is defined as the study medication the following parts of the PK-PPS definition were further clarified: "subjects in the SS-iv" instead of "subjects in the SS" and "infusion times" instead of "intake times". Furthermore, the term "without important protocol deviations impacting the interpretability of the PK analyses" was added to the definition of PK-PPS.

Vital sign and ECG summary tables will summarize the subject data for each timepoint but not as stated in the protocol (pre-bolus/infusion period, the bolus/infusion period, the period immediately post-bolus/infusion, and period between each subsequent bolus/infusion). Adverse events tables will not summarize the subject data as specified in the protocol (pre-bolus/infusion period, the bolus/infusion period, the period immediately post-bolus/infusion, and period between each subsequent bolus/infusion). Instead AEs will be summarized by time relative to most recent bolus/infusion start time ( $\leq 5$  minutes,  $> 5$  to  $\leq 15$  minutes,  $> 15$  to  $\leq 60$  minutes,  $> 60$  minutes to  $\leq 12$  hours and  $> 12$  hours).

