The following summaries will also be produced by country of enrollment (Hungary and rest of the World) for all subjects, by infusion duration and by subject group for the SS-iv:

- Incidence of AEs – Overview
- Incidence of TEAEs

The following summary will also be produced by country of enrollment (Hungary and rest of the World) for all subjects and by infusion duration for the SS-iv:

- Incidence of TEAEs by Maximum Intensity

The following summaries will be produced overall and by age cohort and study period, for all subjects and separately by infusion duration and subject group for the SS:

- Incidence of TEAEs by Study Period
- Incidence of TEAEs Leading to Study Discontinuation by Study Period
- Incidence of Serious TEAEs by Study Period

The following summaries will be produced overall and by age cohort and study period, for all subjects and by infusion duration for the SS:

- Incidence of TEAEs by Maximum Intensity by Study Period

- Incidence of TEAEs by Maximum Relationship by Study Period

The following TEAE summaries will be produced overall and by age cohort for the SS:

- Incidence of Serious TEAEs - Subject Numbers
- Incidence of TEAEs Leading to Study Discontinuation - Subject Numbers

Additionally, incidence of TEAEs will be summarized by categorized relative time infusion for all subjects, and by age cohort for the SS-iv. The time of each AE relative to the start of the previous iv infusion will be calculated as described in [Section 3.2.4](#) and categorized into 0- $\leq$ 5 minutes,  $>5 - \leq 15$  minutes,  $>15$  to  $\leq 60$  minutes,  $>60 - \leq 12$  hours and  $>12$  hours.

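### SAP 10.2.1 omits infusion duration from the only TEAE table by time since infusion start, so as written the table mixes the bolus with the 15-minute infusion

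*SAP*

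**What the plan says.** Protocol 12.4 planned AE reporting tied to each administration: "Safety data will be reported in epochs that include the pre-bolus/infusion period(s), the bolus/infusion period(s"), followed by the time immediately after and the time between doses. Protocol 12.4.1 adds the layout: "Descriptive statistics for the safety variables will be presented by cohort and infusion duration, cohorts overall, and all subjects overall".

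SAP 3.10 openly drops those epochs: "Instead AEs will be summarized by time relative to most recent bolus/infusion start time". The categories are ≤5 minutes, >5 to ≤15 minutes, >15 to ≤60 minutes, >60 minutes to ≤12 hours, and >12 hours. The section says nothing about no longer separating the two modes.

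SAP 10.2.1 specifies the resulting table: "incidence of TEAEs will be summarized by categorized relative time infusion for all subjects, and by age cohort for the SS-iv". The other SS-iv AE summaries in that section (overview, TEAEs, serious TEAEs, discontinuations, intensity, relationship, and the by-country versions) all name infusion duration.

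SAP 3.1 sets a general rule: "All summaries, unless otherwise stated, will be presented overall for all subjects, by age cohorts", and by infusion duration.

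**The concern.** The study evaluates two rates of delivery, and AEs are a primary safety variable. The only planned summary showing when AEs begin relative to dosing is the table in question. About half of each age cohort receives each mode, so the age-cohort columns are mixed as well as the overall column.

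If the table is produced as 10.2.1 words it, two things follow. An early event confined to one mode appears at about half its true frequency, with nothing to show which mode it belongs to. And the same row describes different phases of dosing for different children, because delivery ends at 2 minutes or less in one mode and at about 15 minutes in the other.

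**Working it through.** **Inputs**
- Infusion: 15 minutes ± 3, so it ends 12 to 18 minutes after the start (Protocol 1; note to Table 7-1).
- Bolus: ends at 2 minutes or earlier (same places).
- Bin edges: 5, 15 and 60 minutes, then 12 hours, counted from the start of the previous infusion (SAP 3.10, 10.2.1 and 3.2.4).
- Subjects: about 50, planned as 4 cohorts of about 12, half per mode (Protocol 1 and 12.8).

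The plan gives no power or precision figure to reproduce. Its headcount is consistent: 4 × 12 = 48, against approximately 50. That gives 24 to 25 per mode and 12 / 2 = 6 per cohort and mode.

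**Step 1: is the table split by mode?** SAP 10.2.1 lists all subjects and age cohort. Every other SS-iv AE summary there adds infusion duration in so many words. Two SS tables in the same section (subject numbers for serious TEAEs and for discontinuations) also list only overall and age cohort, so leaving out mode is not unknown in that section. The SAP 3.1 rule applies unless a section states otherwise. The natural reading of 10.2.1 is a pooled table; the other reading is possible.

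**Step 2: do the bins separate during from after?** The share of a bin that falls during dosing is

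max(0, min(end of dose, upper edge) − lower edge) / (upper edge − lower edge).

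| Mode and end of dose | 0 to 5 min | >5 to 15 min | >15 to 60 min |
|---|---|---|---|
| Bolus, 0.5 min | 0.5/5 = 10% | 0% | 0% |
| Bolus, 1 min | 1/5 = 20% | 0% | 0% |
| Bolus, 2 min | 2/5 = 40% | 0% | 0% |
| Infusion, 12 min | 100% | 7/10 = 70% | 0% |
| Infusion, 15 min | 100% | 10/10 = 100% | 0% |
| Infusion, 18 min | 100% | 100% | 3/45 = 6.7% |

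The 0.5 and 1 minute rows are assumed run times; the protocol fixes only the 2-minute ceiling. For the infusion, the 15-minute edge is where dosing nominally stops. Table 5-2 says of that time point: "To be conducted at the end of infusion". For the bolus there is no such edge. In the second bin the infusion is 70% to 100% during dosing and the bolus 0%.

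**Step 3: what does pooling do to a mode-specific signal?** The pooled rate is (events in bolus + events in infusion) / (total subjects). With hypothetical counts of 3/25 = 12.0% and 0/25 = 0%, the table shows 3/50 = 6.0%. With equal groups, an event seen in one mode only is always shown at half its rate.

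**Step 4: what does splitting cost in precision?** The true per-subject rate at which at least one event is seen with 95% probability is 1 − 0.05^(1/n):
- n = 50: 5.8%
- n = 25: 11.3% (n = 24: 11.7%)
- n = 6: 39.3%

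**The case against.** The best defence is SAP 3.1: a general default to split by infusion duration, with 10.2.1 merely silent on mode. This stands in part. Pooling is the natural reading, not a certainty, and the defect may be only a conflict between two sections. A programmer would still have to choose between them.

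Second, mode-specific safety is shown elsewhere. TEAEs overall and by study period are split by infusion duration. Vital signs and ECG are summarized by scheduled time point and mode, including a time point at ≤2 minutes for the bolus. AE listings carry the time since the previous infusion start. So a reader should not infer that acute tolerability by mode is unrecoverable. But none of these is a summary of AE onset time by mode.

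Several stronger readings are tempting and are not supported:
- That the bins fit neither mode. The 15-minute edge fits the infusion; only the ±3 minute window blurs it.
- That the staggered DMC review exists because early reactions are expected to differ by mode. The documents say only that safety and available PK data are reviewed. Protocol 5.3 reports a similar AE profile for both modes in the adult iv study.
- That subjects who receive oral brivaracetam before the first infusion have pre-infusion TEAEs by definition. They can have them. Such events have no previous infusion and hence no bin, though they do appear in the tables by study period.
- That the clock bins should be replaced by bins starting at the end of dosing. The existing edges match scheduled assessment times shared by both modes. A bin from end of dose to 15 minutes after start would be empty for infusions ending at or after 15 minutes, and dosing that ran past 15 minutes would overlap the next bin.

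The small cell sizes are real (Step 4), but the table is descriptive and no test is planned.

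**Conclusion.** The point holds as a gap in the specification. As worded, SAP 10.2.1 presents the only TEAE table by time since infusion start without the split that Protocol 12.4.1 plans and the neighbouring tables carry, and SAP 3.10 does not declare that change. If it is run that way, a mode-specific early event is shown at half its rate, the second bin means different things in the two modes, and no row isolates events during a bolus.

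This rests on reading the specific list in 10.2.1 as overriding the default in 3.1, on roughly equal numbers per mode, and on run times within the protocol's limits. If 3.1 is held to govern, the mixing disappears. The ambiguity in wording and the missing cut at the end of the bolus remain. The matter is worth correcting because the correction is nearly free. It does not undermine the other safety tables.

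**What to change.** In SAP 10.2.1, state that this table is presented by infusion duration, overall and by age cohort. Keep the existing clock bins. Add, for each mode, a separate row classifying onset as during administration or after its end, using the stop time of the relevant dose. Protocol 7.7 already has start and completion times recorded for every iv dose.

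Optionally, give TEAEs before the first iv infusion their own row, and footnote that the >12 hour category includes follow-up events. That category has no upper limit, and for subjects who down-titrate it can reach into up to 4 weeks of down-titration and the 2-week BRV-free period.

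The cost is a sentence or two of SAP text and extra columns and rows in one table, with no new data. The downside is thin cells: about 24 to 25 subjects per mode and about 6 per cohort and mode. The cohort-by-mode columns should therefore be read as counts rather than rates.

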### 10.2.2 AE Listings

All AEs reported during the study will be provided in subject data listings for the SS. These listings will include, but is not limited to AE onset date and time, relationship to study medication and whether the AE is of special interest. AE's of special interest are a selection of adverse events, of particularly interest for this study chosen prior to first subject in, and are captured in the CRF.

The following AE listings will be provided:

- Glossary table for all AEs, where the terms included on the table should match those presented in other AE displays
- All AEs
- All serious AEs
- All AEs leading to study discontinuation
- Listing of all deaths
- TEAEs of interest
- All AEs which worsened during the study (The definition of “worsened” is when the AE is still present but at a heightened intensity.)
- TEAEs in relation to previous PCSTs (Listing will contain PCST of each type that occurred from vital signs, ECG and laboratory values in relation to the time prior to the onset of each AE which occurred after the respective PCST (see [Section 3.2.9](#))).

Should it occur, any uncoded AEs should be designated as “UNCODED CLASS” at all MedDRA levels, and such AEs should be included in summary tables and subject data listings based on this classification (eg, SOC and PT set to UNCODED CLASS).

### 10.3 Medical procedures

Medical procedures prior to study entry and during the study will be listed separately.

### 10.4 Clinical laboratory evaluations

#### 10.4.1 Hematology, Chemistry and Urinalysis Parameters

Laboratory values will be collected according to the protocol schedule of study assessments. In case a laboratory test is repeated at one visit, the latest measurement will be used for summary

tables. For continuous laboratory variables (including hematology and chemistry) summary statistics of Baseline values, Visit 13 values, and change from Baseline will be presented overall and by age cohort, for all subjects, and by infusion duration at each study visit for the SS-iv. For categorical urinalysis laboratory variables summary statistics of Visit 1 and Visit 13 values will be presented overall and by age cohort, for all subjects, and by infusion duration for the SS-iv.

Shifts from Baseline to Visit 13 based on the normal range (ie, low, normal, high, and missing) for each hematology, and chemistry lab parameter will be presented for subjects who have a Baseline and Visit 13 measurement overall and by age cohort, for all subjects and by infusion duration for the SS-iv. Shifts from Baseline to Visit 13 based on the categorization of each urinalysis lab parameter will be presented for subjects who had done a Baseline and Visit 13 measurement, overall and by age cohort, for all subjects and by infusion duration for the SS-iv.

The number and percentage of subjects with possibly clinically significant treatment-emergent (PCST) for each laboratory variable (i.e. PCST low value, PCST high value) for hematology, biochemistry (including Thyroxine (T4)) and urinalysis will be summarized overall and by age cohort, for all subjects, and by infusion duration. The criteria for a laboratory value to be PCST is defined in [Appendix 12.2](#), but note, only laboratory variables that meet PCST criteria at Visit 13, but not Baseline will be considered as PCST.

The number of occurrences of each unique PCST type will be tabulated by timepoint within each visit within each subject, and include relevant criterion: gender, age, race, timepoint, visit, subject group and infusion duration. In addition, the number of subjects with at least one PCST will be displayed for each age cohort.

The following listings will be provided: all laboratory results of clinical chemistry, hematology, urinalysis including an indicator as to which met the criteria for PCST. A separate listing will contain all additional laboratory tests performed and sample takes.

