8.5 TC-2

Telephone Contact-2 is only applicable to subjects who participate in the Down-Titration Period for more than 2 weeks; TC-2 should be conducted approximately half way through the Down-Titration Period.

- Concomitant medications including AEDs
- AEs
- Withdrawal criteria

8.6 Visit 13

This visit is applicable only to subjects who have participated in the Down-Titration Period or to subjects who need to withdraw from the study and do not need to have BRV down titrated.

- Concomitant medications including AEDs
- Physical examination (brief)
- Neurological examination (brief)
- Body height
- Vital signs (BP, pulse rate, RR, and temperature)
- 12-lead ECG
- Clinical chemistry, hematology, and endocrinology
- Urinalysis for subjects for whom urine sample collection is feasible
- Pregnancy testing for females of childbearing potential (urine test)
- AEs
- C-SSRS (for subjects ≥ 6 years of age); version per [Section 10.3.3](#)
- Collect oral BRV

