##### 2.2.2.2 Other safety variables

- 12-lead ECG values before, during, and after each iv BRV administration
- Blood pressure (BP), pulse rate, respiratory rate (RR), and temperature values before, during, and after each iv BRV administration
- Clinical laboratory parameters (hematology, chemistry, and endocrinology) pre and post treatment
- Urinalysis parameters pre and post treatment

Post treatment parameters will be only available for subjects who down titrate and perform Visit 13 assessments.

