A complete set of listings containing all documented data and relevant derived data (eg, change from Baseline) will be generated. Summary tables will only contain data from subjects and visits which have been foreseen by the protocol, eg. in the event data will be captured after TC-1 when it is not required, this data will only be listed and not summarized.

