### 3.4 Definition of Baseline values

Baseline for laboratory variables (blood chemistry, hematology, and endocrinology), vital signs, body weight, and quantitative electrocardiography (ECG) variables is defined as the latest assessment prior to the first infusion of iv BRV. Both scheduled and unscheduled assessments from the central laboratory are considered.

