All vital signs measurements (scheduled and unscheduled) which are taken after the first BRV medication during the EP0065 study will be assessed to determine if they meet PCST criteria. The number and percentage of subjects that meet the criteria for any PCST value, a high PCST value and a low PCST value at each timepoint and visit will be presented for each variable individually overall and by age cohort for all subjects and by infusion duration. A separate summary will be presented by country of enrollment (Hungary and rest of the World) for all subjects and by infusion duration. Percentages will be relative to the number of subjects with a value at each corresponding timepoint or visit.

The number of occurrences of each unique PCST type will be tabulated by timepoint within each visit for each subject, and include relevant criteria: gender, age, race, timepoint, visit, subject group and infusion duration. In addition, the number of subjects with at least one PCST will be displayed for each age cohort.

A subject data listing of all vital sign values will be presented. The listing will contain columns indicating which values met the criteria for PCS and PCST. All body weight values will be listed and will contain a column indicating the PCS and PCST criteria.

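### Laboratory PCST is judged at Visit 13 only, so an abnormal value from an unscheduled draw after iv BRV, or one that is normal on same-visit repeat, is left out of the laboratory PCST summary

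*SAP*

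**What the plan says.** On laboratory variables, SAP 10.4.1 states that "only laboratory variables that meet PCST criteria at Visit 13, but not Baseline will be considered as PCST". On repeats it says: "In case a laboratory test is repeated at one visit, the latest measurement will be used for summary" tables. SAP 3.1 adds a general limit: "Summary tables will only contain data from subjects and visits which have been foreseen by the protocol".

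Protocol Tables 5-1 and 5-4 schedule blood tests and urinalysis only at Visit 1 and Visit 13. Protocol 8.6 says of Visit 13: "This visit is applicable only to subjects who have participated in the Down-Titration Period", or to those who withdraw without needing down-titration. SAP 2.2.2.2 accepts the consequence: "Post treatment parameters will be only available for subjects who down titrate and perform Visit 13 assessments".

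The neighbouring rules are wider:
- Vital signs (SAP 10.5.1): "All vital signs measurements (scheduled and unscheduled) which are taken after the first BRV medication during the EP0065 study will be assessed" against the PCST criteria. SAP 10.5.2 applies the same rule to ECG.
- Baseline (SAP 3.4) is the latest assessment before the first iv infusion: "Both scheduled and unscheduled assessments from the central laboratory are considered".
- Urinalysis (SAP Appendix 12.2.3) defines PCST as an upward shift of at least 2 degrees under treatment and does not mention Visit 13.

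The SAP also plans a listing of all laboratory results with a PCST indicator and a separate listing of additional tests (10.4.1). It plans a PDILI summary at any visit that includes local results, but the PDILI listing covers Visit 1 or Visit 13 only (10.4.2).

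**The concern.** The laboratory rule does not fit the rules around it. An unscheduled abnormal value before the first infusion can become Baseline and so cancel a later PCST. An unscheduled abnormal value after the infusion can never create one. The same child's unscheduled blood pressure or ECG would be screened.

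Unscheduled draws are foreseeable. Protocol 8.8 allows extra assessments at an Unscheduled Visit, and Protocol 10.2.1 requires abnormal hepatic tests to be repeated and monitored. Children who continue into the long-term study have no Visit 13, so an unscheduled draw may be their only laboratory result after iv BRV.

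A second output is affected. The listing in SAP 10.2.2 that sets TEAEs against earlier PCSTs is meant to include laboratory PCSTs. Visit 13 comes after the iv PK Period, so no laboratory PCST can precede a TEAE that starts in that period. For laboratory values, that part of the listing is empty by construction.

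**Working it through.** The documents give no figure on this point to reproduce. The check applies the rules to six cases and then does the cell-size arithmetic.

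**Step 1: the rules as logic.**
- SAP 10.4.1: PCST = 1 if the latest Visit 13 value is abnormal and Baseline is not.
- Comparison rule: PCST = 1 if any value after the first iv dose (scheduled, unscheduled or repeat) is abnormal and Baseline is not.

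| Case | SAP 10.4.1 | Any value after first iv dose |
|---|---|---|
| Single abnormal Visit 13 value | 1 | 1 |
| Visit 13 abnormal, then normal on same-visit repeat | 0 | 1 |
| Visit 13 normal, then abnormal on same-visit repeat | 1 | 1 |
| Unscheduled value abnormal, Visit 13 normal | 0 | 1 |
| Unscheduled value abnormal, no Visit 13 | 0 | 1 |
| Abnormal at Baseline and at Visit 13 | 0 | 0 |

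Three of the six cases differ. Two involve unscheduled draws and one involves a same-visit repeat. In the two unscheduled cases the value is not a PCST by definition, so it also loses the PCST indicator and drops out of the listing of TEAEs in relation to previous PCSTs. In the repeat case the latest-value rule is worded for summary tables. The listing is affected in that case if the PCST flag is derived from the same selected value.

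**Step 2: weight of one uncounted child.** The plan has about 12 subjects per cohort, half on each infusion duration, so 12/2 = 6 per cell.
- Cohort: 1/12 = 8.3%
- Cohort-by-duration cell: 1/6 = 16.7%

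These are weights per case. The documents do not say how many unscheduled abnormalities to expect.

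**Step 3: the denominator.** SAP 10.5.1 and 10.5.2 base PCST percentages on subjects with a value. SAP 10.4.1 gives no denominator, which leaves only the general wording in SAP 3.1. Assume that m of 50 SS-iv subjects have Visit 13 (m is not in the documents). One case is then 100/50 or 100/m percent. With no cases, the one-sided 95% upper limit is 1 − 0.05^(1/n).

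| n | One case | Upper limit, no cases |
|---|---|---|
| 50 (all SS-iv) | 2.0% | 5.8% |
| m = 30 | 3.3% | 9.5% |
| m = 20 | 5.0% | 13.9% |
| m = 10 | 10.0% | 25.9% |
| m = 5 | 20.0% | 45.1% |

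A zero over 50 and a zero over the children actually tested say very different things, so the denominator has to be stated.

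**The case against.** The strongest defence comes from the design. The protocol defines laboratory variables as pre and post treatment, but ECG and vital signs as before, during and after each iv dose. Visit 13 is the one scheduled post-treatment sample. A rate at that visit comes from planned testing, whereas for-cause draws come from children with a suspected problem, and pooling the two mixes different things. This stands as a reason to keep the Visit 13 count. It is not a reason to have no count of the other values.

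The safety net is also real. Every result is listed. PDILI is summarised at any visit. Protocol 10.1.1.1 lets an abnormal laboratory finding be an AE, so it may appear in the TEAE tables.

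A reader might therefore infer too much:
- **That the abnormalities are reported as zero or lost.** They are absent from the PCST count, but the values remain in the listings.
- **That the PCST table is the only incidence summary of post-dose laboratory abnormality.** The PDILI summary and the TEAE tables are others.
- **That the repeat rule must bias the count downward.** It covers repeats within one visit only, and a later abnormal repeat is counted. A downward tilt needs abnormal results to be repeated more often. The protocol requires such post-dose repeats for hepatic tests only.
- **That every child without Visit 13 counts as a zero.** That depends on the unstated denominator.

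Copying the vital-sign rule unchanged would also be wrong. SAP 10.5.1 assumes that OLB and RxB subjects took BRV on the first day of screening. Anchoring on the first BRV dose would let an abnormal screening sample that was normal before infusion become treatment-emergent. It would also put nearly all of these subjects into the denominator through Visit 1.

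**Conclusion.** The point holds as a gap in one descriptive table and in the listing of TEAEs in relation to previous PCSTs. Followed as written, SAP 10.4.1 never counts an unscheduled abnormality after iv BRV as a laboratory PCST, and it does not count a Visit 13 abnormality that is normal on same-visit repeat. Neither SAP 10.4.1 nor SAP 3.10 explains the difference from vital signs and ECG.

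The gap is mainly in parameters outside the PDILI criteria, which use only ALT, AST and total bilirubin (SAP Appendix 12.3). Creatinine, eosinophils and urinalysis are examples. They are relevant because Protocol 10.1.1.3 names five nephritis terms among the AEs of special interest.

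The size cannot be estimated. The figures of 8.3% and 16.7% rest on cells of 12 and 6 and on one assumed case. The primary safety variables, AEs and withdrawals due to AEs, are not affected.

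**What to change.** In SAP 10.4.1:
1. Define laboratory PCST as any scheduled, unscheduled or repeat value after the first iv BRV dose that meets the PCS criteria when the Baseline value did not. Use the worst value, taken separately for low and high criteria.
2. State the denominator: subjects with at least one laboratory value after the first iv dose.
3. Keep the Visit 13-only count alongside, so that scheduled and for-cause testing can be told apart.
4. Keep the latest-repeat rule for mean, change and shift tables only.

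Elsewhere, exempt this table from the SAP 3.1 limit on summary data, bring the urinalysis wording in Appendix 12.2.3 into line, and extend the PDILI listing in SAP 10.4.2 to any visit to match its summary.

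The cost is SAP wording and minor programming, with no new data. For-cause draws may raise the reported rates slightly, and the Visit 13-only count lets a reader see that.
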